### 8.3 PREMATURE DISCONTINUATION AND MISSING DATA

#### 8.3.1 Missing Data Handling for 6MWD

For the analysis of 6MWD, subjects may not have completed the treatment with study drug prior to the Week 16 visit for the following reasons: death, progressive disease, AE, withdrawal of consent by the subject, protocol violation, loss to follow-up, termination of study by the sponsor, or withdrawal for other reasons. Every attempt must be made to perform all efficacy assessments immediately prior to premature termination of study drug or withdrawal from the study. In addition, subjects still receiving study drug may be too critically ill to perform the 6MWT, resulting in missing data for that assessment.

Every effort should be made to complete all scheduled study assessments for all randomized subjects. Although attempts will be made to continue to collect data after termination of study drug, these data are being collected for sensitivity analyses and descriptive purposes only. Assessments performed after treatment unblinding or more than 24 hours after the last dose of study drug will not be included in the main analyses of peak 6MWD.

For subjects whose peak 6MWD measures at Week 4, Week 8, Week 12, or Week 16 are missing, the missing value will be imputed as described in Table 8-1.

Reason for missing 6MWD measure	Imputation
Death (all causes)	Worst score (0 meters)
Clinical worsening event	Worst score (0 meters)
Too ill to perform 6MWT	Worst score (0 meters)
All other reasons	Last (peak) Observation Carried Forward (LOCF)

Table 8-1Imputation Rules for Peak 6MWD

Abbreviations: 6MWD, 6-Minute Walk Distance; 6MWT, 6-Minute Walk Test.

For subjects whose trough 6MWD measures at Week 15 are missing, the missing values will be imputed as described in Table 8-2.

Reason for missing 6MWD measure	Imputation
Death (all causes)	Worst score (0 meters)
Clinical worsening	Worst score (0 meters)
Too ill to perform 6MWT	Worst score (0 meters)
All other reasons	Baseline Observation Carried Forward (BOCF)

Table 8-2Imputation Rules for Trough 6MWD

Abbreviations: 6MWD, 6-Minute Walk Distance; 6MWT, 6-Minute Walk Test, BOCF, Baseline observation carried forward.

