10.3.1 Primary Efficacy Endpoint

The primary efficacy endpoint is the change in 6MWD measured at peak exposure from Baseline to Week 16. This study hypothesizes that inhaled treprostinil will improve exercise capacity after 16 weeks of therapy as compared with placebo when administered to subjects

with PH associated with ILD including CPFE. Non-parametric analysis of covariance will be used to estimate the treatment effect. The magnitude of treatment effect will be estimated with the Hodges-Lehmann median difference between 2 treatment groups. For subjects who discontinue from the study early, the last observation carried forward method will be used to impute the 6MWD at Week 16.

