# 5 SAMPLE SIZE CONSIDERATIONS

Using an allocation ratio of 1:1 between inhaled treprostinil and placebo, a sample size of approximately 266 subjects (133 per treatment) would provide at least 90% power at a significance level of 0.05 (2-sided hypothesis) to detect a 30 meter between-treatment difference in the change from Baseline to Week 16 in 6MWD, assuming a standard deviation of 75 meters.

The total sample size will be approximately 314 subjects to account for a discontinuation rate of approximately 15%.

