# **10.1 PRIMARY EFFICACY MEASURES**

# 10.1.1 Primary Efficacy Analyses

# 10.1.1.1 Hypothesis

The primary efficacy endpoint of peak 6MWD assesses if inhaled treprostinil will increase the distance traversed in the peak 6MWT at Week 16 over placebo in subjects with PH-ILD. The null and alternative hypotheses are:

$$H_0: \mu_1 = \mu_2$$
$$H_a: \mu_1 \neq \mu_2,$$

where  $\mu_1$  and  $\mu_2$  are the median change from Baseline in 6MWD of the inhaled treprostinil and placebo treatment groups, respectively.

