# 10.1.1.2 Primary Efficacy Analysis

All 6MWT data will be listed for all subjects. For each scheduled assessment, this listing will include the date test was performed (or date test was intended to be performed if subject is unable to attempt the test), start time of the test, nominal time point, last treatment dose, hours from last treatment dose to 6MWT start, if walk was attempted, total distance walked (in meters), whether subject received oxygen during the test, amount of supplemental oxygen, and any circumstances that adversely affected the walk (if any) including reason for not

attempting test (if any). The trough 6MWT measure will also be indicated. In addition, a listing of 6MWD with imputed values will be included for both peak and trough 6MWD data.

For the primary efficacy analysis, the effect of inhaled treprostinil versus placebo on change in peak 6MWD at Week 16 will be evaluated via analysis of covariance (ANCOVA). Change from Baseline in peak 6MWD is the dependent variable, and treatment and Baseline 6MWD are covariates in this ANCOVA model. Least squares means and standard errors for each treatment group, the least squares mean difference and its standard error, as well as a 95% confidence interval for the treatment group difference and p-value for treatment group comparison will be calculated from the ANCOVA model. This methodology will be carried out as follows:

- 1. Walk distances obtained after study drug termination or unblinding will be excluded (as described in Section 8).
- 2. Imputation rules in Table 8-1 will be applied.
- 3. The LOCF algorithm will be applied.
- ANCOVA will be conducted based on the pseudo SAS code: proc glm; class Treatment; model DistC = Treatment Dist0; run;

where DistC is the change from Baseline in peak 6MWD at Week 16 and Dist0 is the baseline measure of the 6MWD.

If the ANCOVA assumptions are violated, the primary efficacy analysis will be based on non-parametric analysis of covariance within the framework of the extended Cochran-Mantel-Haenszel test (Koch 1990, Koch 1998, Stokes 2000). Specifically, a Cochran-Mantel-Haenszel mean score test will be used on the standardized mid-ranks (ie, overall rank divided by the number of ranks +1, or "modified ridit" scores) of the residuals from an ordinary least squares regression with change from Baseline in peak 6MWD at Week 16 as a linear function of distance walked at Baseline (as a continuous variable). This methodology will be carried out as follows:

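### Missing walks scored 0 m go first into a mean-based ANCOVA: depending on event rates this costs power or turns events into metres, and the switch to the protocol's rank analysis has no stated trigger

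*SAP*

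**What the plan says.** - **Scoring.** SAP 8.3.1, Table 8-1, gives "Worst score (0 meters") when the peak walk is missing because of death, a clinical worsening event or being too ill to walk. Other missing walks are carried forward. Walks after unblinding or more than 24 hours after the last dose are left out of the main analysis, and SAP 10.1.1.3 imputes excluded values by the same rules.
- **First-line model.** SAP 10.1.1.2: "Change from Baseline in peak 6MWD is the dependent variable, and treatment and Baseline 6MWD are covariates in this ANCOVA model". The output is a least-squares mean difference.
- **Fallback.** The same section makes a rank-based ANCOVA primary, with Wilcoxon and Hodges-Lehmann added, if the ANCOVA assumptions are violated. It does not say which assumptions, which test or which threshold.
- **Hypothesis.** SAP 10.1.1.1: the two parameters "are the median change from Baseline in 6MWD of the inhaled treprostinil and placebo treatment groups, respectively".
- **Protocol 10.3.1.** Non-parametric ANCOVA is the primary method, with last observation carried forward and no 0 m rule. "The magnitude of treatment effect will be estimated with the Hodges-Lehmann median difference between 2 treatment groups".
- **Sample size.** SAP 5 sizes the trial "to detect a 30 meter between-treatment difference in the change from Baseline to Week 16 in 6MWD" with 90% power or more at a 2-sided 0.05 level. The only input on variability is "assuming a standard deviation of 75 meters". No event rate or allowance for 0 m scores is mentioned.
- **Sensitivity analyses.** SAP 10.1.1.3 repeats the analysis with LOCF, last rank carried forward and observed values, but only if the primary result is significant.

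**The concern.** A 0 m score is a way of ranking a bad outcome last. Least squares treats it as a measured distance: the subject's change becomes minus the whole Baseline walk, which is at least 100 m by eligibility and more than 350 m in the upper stratum. A small share of such values can inflate the residual variance well beyond 75 m, and any imbalance between arms is reported as metres walked.

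The primary test also gates every secondary test (SAP 8.4), and SAP 10.2.1 and 10.2.3 reuse its method for Week 12 and for the trough walk. If the result were lost to variance created by the zeros, the planned LOCF, last-rank and observed-value analyses that would show this would not be run.

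**Working it through.** **1. The plan's own figure.** Inputs from SAP 5: difference 30 m, SD 75 m, 2-sided 0.05, 90% power, 1:1.

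- n per arm = 2 × (1.960 + 1.2816)² × (75/30)² = 2 × 10.507 × 6.25 = 131.3, so 132. The stated 133 per arm gives 90.4%.
- 266 / 0.85 = 313, against 314 stated. The figure is reproduced.
- Imputation keeps treated subjects in the analysis, so about 157 per arm are analysed. SE = 75 × √(2/157) = 8.46, 30/8.46 = 3.54, power = Φ(3.54 − 1.96) = 94%.

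**2. Assumptions not in the documents.** Baseline mean m = 200, 260 or 350 m, Baseline SD 90 m, and share p scored 0 m.

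**3. Equal rates in both arms, true effect 30 m.** Given Baseline, the Week 16 value is 0 with probability p and otherwise the walk. Ignoring the 100 m floor:

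- mean difference = (1 − p) × 30
- residual variance = (1 − p) × 75² + p(1 − p) × Q, with Q = [m² + (m + 30)²]/2 + 90² = 54,550 / 83,950 / 141,550

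Example, p = 5%, m = 260: 0.95 × 5,625 + 0.0475 × 83,950 = 9,331, so SD = 96.6 and SE = 96.6 × √(2/157) = 10.90. Then 28.5/10.90 = 2.61 and power = Φ(0.65) = 74%.

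Power in %, for m = 200 / 260 / 350 m. Simulations used 2,000 trials per scenario; the rank test follows the SAP's SAS code.

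| Scored 0 m per arm | ANCOVA, formula | ANCOVA, simulated | Rank test, simulated |
|---|---|---|---|
| 0% | 94 / 94 / 94 | 94 to 95 | about 93 |
| 2% | 89 / 87 / 82 | 89 / 86 / 83 | about 91 |
| 5% | 81 / 74 / 63 | 80 / 74 / 62 | 89 / 88 / 86 |
| 10% | 67 / 57 / 43 | 67 / 57 / 43 | 81 / 81 / 79 |

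A second simulation gave 88/87/80, 78/76/62 and 59/53/43 for ANCOVA in the last three rows, and about 91, 87 to 88 and 78 to 80 for ranks. Most cells agree within about 4 points. The largest gap is 8 points (10%, m = 200), where the formula supports the higher value. At p = 5% and m = 260, moving the Baseline SD from 60 to 120 m changes ANCOVA power only from 76 to 72%.

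Restoring 90% power for ANCOVA at p = 5% needs n = 2 × 10.507 × (SD/difference)². With simulated SDs of 88.6 / 96.0 / 109.9 and differences of 28.2 / 28.5 / 28.4, that is about 208 / 239 / 315 per arm.

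**4. Unequal rates: 10% placebo, 5% active.**

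- No walking effect: the mean difference is (0.10 − 0.05) × m = 10 / 13 / 17.5 m. Simulated ANCOVA gives 10 / 13 / 17 m and Hodges-Lehmann about 7 to 8 m.
- True 30 m effect: ANCOVA power is 96 / 95 / 91%. At m = 260 the expected difference is 0.95 × 30 + 0.05 × 260 = 41.5 m (simulated 41.7 m; Hodges-Lehmann 37.7 m).

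**5. Is the change scale to blame?** With Baseline as covariate, ANCOVA of change and ANCOVA of raw Week 16 distance gave the same treatment estimate on one simulated data set (26.24 m in both), as algebra requires. The cause is zeros in a mean.

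**The case against.** **The rank analysis is already in the SAP.** This is the strongest reply, and a reader of the first-line model alone might wrongly infer that no robust analysis exists. A cluster of zeros is just what an assumption check should catch. If a Shapiro-Wilk test on the residuals were the trigger (the SAP names none), it would reject in 93% of simulated trials at 2% scored 0 m and in nearly all at 5%. What remains is that the switch is undefined. Residuals of a model containing treatment are normally inspected after unblinding, so the choice of primary p-value stays open at the wrong time. If the fallback is the likely outcome, naming it now gives up little.

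**A sharp power loss does not follow in general.** It needs similar rates in both arms, and it is modest at 2%. When active has fewer events, power stays above 90%. Nor is every worsening subject scored 0 m: one with a valid on-treatment walk keeps it. Both points stand.

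**Counting death or inability to walk as failure is a legitimate choice**, and protocol 10.3 lets the SAP record changes of method. This also stands. The objection here is to averaging the score as metres, not to counting the failure.

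**Zero is not always the lowest change.** A reader might infer that the change scale causes the problem, since a death from a 100 m Baseline scores −100 m and a survivor falling from 400 to 250 m scores −150 m. The ordering point is true but has little consequence: step 5 shows the change scale leaves the ANCOVA estimate untouched, and tied worst ranks move rank-test power by less than 1 point.

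**Hodges-Lehmann mixes events and walking too.** Correct: it still reads 7 to 8 m with no walking effect, so the mixing is reduced but not removed.

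**Conclusion.** The point holds in a conditional form. The SAP puts 0 m scores into a mean-based first-line analysis that departs from the protocol's primary method and from its own median hypothesis, has no defined route to the rank analysis, and rests on an SD with no visible allowance for the zeros.

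The size depends on three unstated quantities: the 0 m rate, its balance between arms and the Baseline mean. Over the assumed range, equal rates of 2, 5 and 10% give ANCOVA power of roughly 80 to 89%, 62 to 81% and 43 to 67%. The rank test gives about 91%, 86 to 89% and 78 to 81%. With 10% against 5% favouring active, power is kept, but the reported metres include some 10 to 17 m that nobody walked.

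A reader might conclude that the trial is underpowered or its estimate biased by a known amount. The documents do not support that, because they give no event rate.

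**What to change.** 1. In SAP 10.1.1.2, make the baseline-adjusted rank analysis the primary test without condition, as in protocol 10.3.1, and take the effect in metres from the Hodges-Lehmann estimate. Delete the assumption-triggered switch.
2. Move the least-squares-mean ANCOVA to a sensitivity analysis.
3. Report the number scored 0 m by arm and reason next to the primary result, so that the event part of the effect is visible.
4. In SAP 10.1.1.3, drop the condition that the LOCF, last-rank and observed-value analyses run only after a significant primary result.
5. When promoting the rank test, settle its definition. The SAP text ranks the residuals of a regression on distances, while the code ranks first and then regresses.

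Replacing 0 m by tied worst ranks is optional. If the sponsor prefers ANCOVA as primary, the sample size should instead state a 0 m rate and allow for it.

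Cost: SAP wording and a few lines of code, and about 1 power point if nobody is scored 0 m.

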### 8.3.2 Missing Data Handling for Other Efficacy Assessments

For the secondary endpoints of NT-proBNP, the missing value at Week 16 will be imputed using LOCF. If the NT-proBNP measure at Baseline is missing, the change from Baseline will not be calculated. The subject will not be included in the analyses.

For exploratory endpoints of SGRQ, biomarkers, and DSP, the missing values will not be imputed, and all analyses will be based on the observed cases.

### 8.4 MULTIPLE COMPARISONS AND MULTIPLICITY

The primary efficacy endpoint of change in 6MWD measured at peak exposure from Baseline to Week 16 will be tested at alpha level 0.05. If the primary efficacy endpoint is statistically significant at alpha level 0.05, the statistical tests for secondary efficacy endpoints will be performed.

To control the Type 1 error rate, the secondary efficacy endpoints will be tested using a hierarchical (fixed-sequence) testing procedure. The change from Baseline in peak 6MWD at Week 12 will be tested at a 2-sided Type 1 error rate of 0.05. The subsequent tests for change from Baseline in NT-proBNP at Week 16, and then the change from Baseline in trough 6MWD at Week 15, will be tested sequentially only if the preceding test is statistically significant.

### 8.5 DERIVED AND TRANSFORMED DATA

Time to clinical worsening will be evaluated as an exploratory endpoint from the time to randomization until 1 of the following criteria are met:

- Hospitalization due to a cardiopulmonary indication
- Decrease in 6MWD >15% from Baseline directly related to disease under study at 2 consecutive visits and at least 24 hours apart
- Death (all causes)
- Lung transplantation

Time to clinical worsening is calculated as described in Table 8-3.

Parameter	Scenario	Formula	Status
	Subjects with clinical worsening event reported	= (Worsening date – Randomization date +1)/7	0 (event)
Time to	Subjects who died during the study	= (Death date – Randomization date $+1$ )/7	0 (event)
clinical worsening (weeks)	Subjects without clinical worsening event during the study	= (Last assessment date – Randomization date +1)/7	1 (censored)
	Subjects discontinued from the study prematurely	= (Last assessment date – Randomization date +1)/7	1 (censored)

For subjects with clinical worsening due to decrease from Baseline in 6MWD, a confirmatory 6MWT should be conducted. The event time is based on the date of the confirmatory 6MWT. If the confirmatory 6MWT is not conducted, the event time is then based on the date of the first 6MWT.

Distance Saturation Product (DSP) is calculated as follows:

Parameter	Formula
DSP (m%)	= (Distance walked in meters) x (Lowest oxygen saturation recorded during the 6MWT)

Abbreviations: 6MWT, 6-Minute Walk Test; DSP, Distance Saturation Product.

Adjustments to the QT intervals will be calculated as follows:

Parameter	Formula
QTc (Bazett)	$= Q T/\sqrt{60/HR}$
QTc (Fridericia)	$= Q^{-}T/\sqrt[3]{60/HR}$

Abbreviations: HR, Heart rate; QTc, Q-T interval corrected for heart rate; Q-T, Electrocardiographic interval from beginning of QRS complex to end of the T wave.

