Abbreviations: ECG, electrocardiogram; NT-proBNP, N-terminal pro-brain natriuretic peptide; PFTs, pulmonary function tests; PH, pulmonary hypertension; SGRQ, St. George's Respiratory Questionnaire; 6MWT, 6-minute walk test; 6MWD, 6-minute walk distance; CT, computed topography; SpO₂, saturation of peripheral capillary oxygenation; HR, heart rate; eCRF, electronic case report form; FEV1, forced expiratory volume in 1 second; FVC, forced vital capacity; TLC, total lung capacity; DLCO, lung diffusion capacity; AE, adverse event; SAE, serious adverse event; 6MWD, 6-minute walk distance; ET, early termination

- ^a Screening Visit assessments can occur up to 30 days prior to the first dose of study drug. Baseline assessments can occur up to 48 hours prior to the first dose of study drug to allow for scheduling of all activities; however, the Baseline 6MWT must be performed prior to randomization. Screening and Baseline assessments may be combined if all entry criteria are satisfied within 48 hours prior to the first dose of study drug. Baseline PFTs, 6MWT, and CT scan (if a historical scan within 6 months is not available) assessments used to determine eligibility criteria must be performed prior to randomization. Sites should provide a completed Pre-Baseline review form to the Medical Monitor which will be reviewed, signed, and returned to the site prior to randomization.
- b The visit window for Week 4, Week 8, Week 12, Week 15, and Week 16 is ± 5 days. The Week 16 visit must occur at least 24 hours after the Week 15 visit.
- c For the Screening and Baseline Visits, the subject must be evaluated for and meet all inclusion/exclusion criteria.
- d Vital signs must be collected after 5 minutes of rest (seated); no other measurements or procedures should be performed during this 5-minute period. When possible, vital signs should be collected prior to the 6MWT. If vital signs cannot be obtained prior to the 6MWT then they should be obtained after recovery from the 6MWT.
- ^e Blood for NT-proBNP assessment must be drawn prior to conducting the 6MWT and will occur prior to randomization at Baseline (or as part of the Screening Visit assessment if the Screening and Baseline Visits are combined).
- f For subjects consenting to the optional biomarker sample.
- g For subjects consenting to the optional whole genome sequencing sample.
- h For females of childbearing potential.

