#### 10.3.3 Time to Clinical Worsening

• Data on the clinical worsening assessment page of the eCRF will be used to determine clinical worsening status. Investigator-reported clinical worsening events including the date (study day) of the event, category of the clinical worsening event, Baseline 6MWD, first 6MWT details, and second 6MWT details will be listed. The time to clinical worsening will be calculated according to the rules described in Table 8-3 in Section 8.5.

The number and percentage of subjects with any clinical worsening and with each category of clinical worsening will be summarized by treatment group. Time to clinical worsening will be summarized by treatment group using product-limit estimates calculated by the Kaplan-Meier method and displayed graphically as Kaplan-Meier curves. A tabular summary of this analysis will include the number of subjects at risk (sample size), estimated median duration, and a 95% confidence interval for the median duration for each treatment group. The log-rank test, adjusted for Baseline 6MWD category, will be used to calculate the p-value for treatment differences in the ITT population.

The SAS Procedure LIFETEST will be used. The pseudo SAS statements are listed below:

proc lifetest; time TimeToWorsening\*Censor\_Status(1); strata B\_6MWD / group = Treatment test=all; run;

where B\_6MWD denotes the categorical Baseline 6MWD variable ( $\leq$ 350 meters versus >350 meters).

In addition, the Cox proportional hazards model will be fit to obtain the hazard ratio and its associated 95% confidence interval. The model will include treatment and Baseline 6MWD as explanatory variables. The SAS procedure PHREG will be used. The pseudo SAS statements are listed below:

where Dist0 denotes the Baseline 6MWD variable (continuous). If it is determined that the proportional hazards assumption does not hold for Baseline 6MWD, a stratified analysis will be conducted. The above SAS code will be amended to remove Dist0 from the model statement and add the 'strata B\_6MWD;' statement.

If the proportional hazards assumption does not hold for the Cox model, the restricted mean survival time (RMST) and its associated standard error will be calculated for each treatment group at Week 16 (Royston 2013). A 95% confidence interval will be constructed for the difference in RMST between the 2 treatment groups at Week 16.

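### SAP 8.5 lets a reported walk decline seen at only one visit count as clinical worsening, although its definition of this exploratory endpoint requires two

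*SAP*

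**What the plan says.** The walk component in SAP 8.5 reads: "Decrease in 6MWD >15% from Baseline directly related to disease under study at 2 consecutive visits and at least 24 hours apart". Protocol 3.3.1.4 and SAP 2.3 and 10.3 give the same two-visit requirement, and none of them states an exception for a missing second walk.

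After Table 8-3, SAP 8.5 says that a confirmatory walk should be done when worsening is due to a walk decline. If it is done, "The event time is based on the date of the confirmatory 6MWT". If it is not, "If the confirmatory 6MWT is not conducted, the event time is then based on the date of the first 6MWT".

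Table 8-3 assigns status by what was reported. The row "Subjects with clinical worsening event reported" has status 0 (event), and the row "Subjects without clinical worsening event during the study" is censored at the last assessment. SAP 10.3.3 names the source: "Data on the clinical worsening assessment page of the eCRF will be used to determine clinical worsening status". For each reported event, the "first 6MWT details, and second 6MWT details will be listed".

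**The concern.** A decline with no second walk cannot be shown to meet a two-visit criterion, yet the SAP gives it an event date. If such a decline is reported, Table 8-3 makes it an event. The two walks are listed, but no step compares them with the definition, and no analysis restricted to confirmed declines is planned.

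Two things follow. A reader told that every walk event was a sustained decline could be wrong about some of them. And one Kaplan-Meier curve could mix two dating conventions: second walk for confirmed declines, first walk for the others. The log-rank test and the Cox model would inherit both.

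The situation is foreseeable. Week 16 is the final visit (Protocol 3.1), so a first decline there has no later scheduled walk. SAP 5 expects about 15% discontinuation. SAP 8.3.1 expects that some subjects will be too ill to walk.

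**Working it through.** **1. The plan's own figures.** The documents give no event count or power for this endpoint, so there is no stated figure to correct. Two inputs are borrowed from the primary sample size in SAP 5: SD of change 75 m and 15% discontinuation. That calculation reproduces. Per arm, n = 2 × (1.960 + 1.282)² × 75² / 30² = 131.4, so 132 against the stated 133; and 266 / 0.85 = 312.9 against about 314.

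**2. Status and date, case by case.**

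| Reported walk decline | Meets the two-visit definition? | Status (Table 8-3) | Date (SAP 8.5) |
|---|---|---|---|
| Second walk done, also >15% down | Yes | Event | Second walk |
| Second walk not done | Cannot be shown | Event | First walk |

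**3. Size of the dating difference.** Scheduled walks fall on days 29, 57, 85, 106 and 113 (Protocol 3.2). Target gaps are 28, 28, 21 and 7 days. With ±5 days on each visit they become 18-38, 18-38, 11-31 and 1-17 days. The last lower limit is 1 day because "The Week 16 visit must occur at least 24 hours after the Week 15 visit". An unscheduled second walk could also follow after 24 hours.

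**4. Is confirmation a formality?** Assume baseline 250 m, no true change and normally distributed change. A fall of more than 15% is more than 37.5 m, with probability Φ(-37.5/75) = Φ(-0.5) = 0.309 at a given visit. For between-visit correlation 0.5, 0.7 and 0.9, the probability of a fall at both of two visits is 0.163, 0.198 and 0.245. The chance that the second walk confirms the first is then 0.53, 0.64 and 0.80. So the second walk matters to what counts as an event.

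**5. How many subjects could the rule reach?** A multivariate normal simulation used 800,000 subjects per scenario and arm, walks on the five scheduled days and exchangeable correlation 0.6, 0.75 or 0.85. Dropout was random and spread evenly over days 1-113, and every decline was assumed reported as disease-related. The rule applies when the last walk attended is more than 15% below baseline, no earlier pair was confirmed and no further walk is done.

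| Baseline 250 m, no true change | r = 0.6 | r = 0.75 | r = 0.85 |
|---|---|---|---|
| Through dropout, all 15% stop walking | 2.11% | 1.89% | 1.72% |
| Same, with an early-termination walk | 2.51% | 2.16% | 1.95% |
| Lone Week 16 decline (upper bound) | 7.62% | 5.72% | 4.23% |

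- Of 314 subjects, 1.72-2.51% is 5 to 8.
- For baselines of 200-350 m, the first row ranges from 1.41% to 2.27% and the second from 1.58% to 2.66%.
- The dropout share is proportional to the fraction who stop walking. If only 5% stop (an assumption), 1.72-2.11% × 5/15 = 0.6-0.7%, about 2 of 314.
- The Week 16 row scales with the fraction who reach Week 16. At 5% it becomes 4.23-7.62% × 0.95/0.85 = 4.7-8.5%.

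**6. Effect on the comparison.** The plan's 30 m difference is set as +15 m against -15 m, with 157 per arm and 15% stopping. The ratio is the proportion with a walk event on treprostinil divided by that on placebo.

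| Walk events counted | Ratio (r = 0.6 / 0.75 / 0.85) | z |
|---|---|---|
| Confirmed only | 0.596 / 0.615 / 0.623 | 2.88 / 2.73 / 2.67 |
| Plus dropout cases | 0.603 / 0.620 / 0.626 | 2.97 / 2.81 / 2.75 |
| Plus all lone Week 16 declines | 0.652 / 0.654 / 0.652 | 2.97 / 2.83 / 2.77 |

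The ratio moves slightly towards 1, and z does not fall.

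**The case against.** **The sentence only dates an event; it does not create one.** It concerns subjects already classed as worsened, and the eCRF page may itself require both walks. This stands in part: the page is not in the documents, so the rule may reach few or no subjects. It does not remove the conflict. A date for the case with no second walk has no use unless such a case can be an event, Table 8-3 scores the report as one, and no check is stated.

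**Counting the decline is defensible.** A second walk may be missing because the subject was too ill, and censoring that subject may be informative. This stands. A reader might infer that censoring unconfirmed declines is the only acceptable main analysis; the documents do not support that. The fault is that definition and rule disagree, not that the rule is indefensible.

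**The 15% overstates missing second walks.** Protocol 7.6 and 8.1 encourage subjects who stop study drug to attend the remaining visits except Week 15. Under Protocol 7.8, those withdrawn from drug for clinical worsening should complete these visits to be eligible for the open-label study. This stands, and is why the 5% scenario is shown. The split between stopping drug and leaving the study is not given.

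**A reader might infer harm to the primary endpoint,** because Tables 8-1 and 8-2 impute 0 m for a walk missing through clinical worsening. The documents do not support that. Those tables act only when the walk is missing and that is the recorded reason, and no text says that an unconfirmed decline would be coded so. SAP 10.1.1.3 also plans LOCF, LRCF, observed-value and MMRM analyses of the primary endpoint, and SAP 10.2.3 an observed-case trough analysis.

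**Conclusion.** The inconsistency is real and minor. Reported one-walk declines could be analysed as events that do not meet the stated definition, on a different dating convention from confirmed ones. It would go too far to say that they do enter the analysis, since this depends on an eCRF page that cannot be seen.

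The sizes in the working rest on the SAP's SD, an assumed baseline and correlation, random dropout and full reporting of declines as disease-related. Full reporting makes them lean high. The Week 16 figure is an upper bound: it needs every lone decline there to be reported with no second walk, although the SAP says that one should be done.

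Nothing here suggests that the rule favours treprostinil: the small shift in the ratio is towards no difference. The endpoint is outside the fixed testing sequence of SAP 8.4, so neither alpha nor the sample size is affected. Confidence is high on the mismatch in the text and low on how often it would matter.

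**What to change.** Reconcile the definition and the rule in SAP 8.5 by one of two routes:

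- **(a) Definition governs.** In the main analysis a walk decline is an event only with a second qualifying walk, scheduled or unscheduled, and is dated at that walk. Otherwise the subject stays in follow-up and is censored at the last assessment, as Table 8-3 does for subjects without an event, unless another component occurs. A sensitivity analysis counts unconfirmed reported declines at the first walk.
- **(b) Rule governs.** The exception and its dating are written into the endpoint definition wherever the SAP states it, and a confirmed-only analysis is added.

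Under either route, add a derivation check against the first and second walk details that SAP 10.3.3 already lists. State also that the clinical worsening entry in Tables 8-1 and 8-2 uses the same definition.

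The cost is a sentence, a cross-reference, the derivation check and one added clinical-worsening output beside Table 14.2.5.1 and Figure 14.2.4. No new data are needed. The downside falls on the confirmed-only analysis, which has slightly fewer events and possibly informative censoring; reporting both versions shows whether that matters.
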